9.6 Statistical Methods

9.6.1 Statistical Methods for Efficacy Analyses

This section describes the statistical methods that address the primary and secondary objectives. Methods related to exploratory objectives will be described in the sSAP.

The stratification factors used for randomization (see Section 6.3.2) will be applied to all stratified analyses, in particular, the stratified log-rank test, stratified Cox model, and stratified Miettinen and Nurminen method [Miettinen, O. and Nurminen, M. 1985]. If there are small strata, for the purpose of analysis, strata will be combined to ensure sufficient number of participants, responses, and events in each stratum. Details regarding the pooling strategy will be pre-specified in the sSAP, prior to the database lock for the first analysis when each applicable endpoint will be analyzed, and decisions regarding the pooling will be based on a blinded review of response and event counts by stratum.

Confidential

22-JAN-2025

9.6.1.1 Overall Survival

The non-parametric Kaplan-Meier method will be used to estimate the survival curves. The hypotheses of treatment difference in survival will be tested by the stratified log-rank test. A stratified Cox proportional hazard model with Efron's method of tie handling will be used to estimate the magnitude of the treatment difference (ie, the HR). The HR and its 95% CI from the stratified Cox model with a single covariate for treatment will be reported. The stratification factors used for randomization will be applied to both the stratified log-rank test and the stratified Cox model. Participants without documented death at the time of analysis will be censored at the date the participant was last known to be alive.

9.6.1.2 Progression-Free Survival (PFS)

The non-parametric Kaplan-Meier method will be used to estimate the PFS curve in each treatment group. The treatment difference in PFS will be assessed by the stratified log-rank test. A stratified Cox proportional hazard model with Efron's method of tie handling will be used to assess the magnitude of the treatment difference (ie, HR) between the treatment arms. The HR and its 95% CI from the stratified Cox model with a single treatment covariate will be reported. The stratification factors used for randomization (See Section 6.3.2) will be applied to both the stratified log-rank test and the stratified Cox model.

Since disease progression is assessed periodically, progressive disease (PD) can occur any time in the time interval between the last assessment where PD was not documented and the assessment when PD is documented. The true date of disease progression will be approximated by the earlier of the date of the first assessment at which PD is objectively documented per RECIST 1.1 by BICR and the date of death. Death is always considered a PD event.

Table 11Censoring Rules for Primary and Sensitivity Analyses of PFS

9.6.1.3 Objective Response Rate (ORR)

The stratified Miettinen and Nurminen's method will be used for the comparison of ORR between 2 treatment groups. The difference in ORR and its 95% CI from the stratified Miettinen and Nurminen's method with strata weighting by sample size will be reported. The stratification factors used for randomization (see Section 6.3.2) will be applied to the analysis. Additional supportive unstratified analyses may also be provided. A sensitivity analysis will be performed for the comparison of ORR based on investigator's assessment.

The point estimate of ORR will be provided by treatment group, together with 95% CI using exact binomial method proposed by Clopper and Pearson (1934) [Clopper, C. J. and Pearson, E. S. 1934].

9.6.1.4 **Duration of Response (DOR)**

If sample size permits, DOR will be summarized descriptively using Kaplan-Meier medians and quartiles. Only the subset of participants who show a confirmed CR or PR will be included in this analysis. Censoring rules for DOR are summarized in Table 12.

For each DOR analysis, a corresponding summary of the reasons responding participants are censored will also be provided.

Table 12Censoring Rules for DOR

9.6.1.5 Analysis Strategy for Efficacy Variables

A summary of the primary analysis strategy for the key efficacy endpoints is provided in Table 13.

Endpoint/Variable	Statistical Method	Analysis Population	Missing Data Approach
Primary Analyses			
OS	Testing: stratified log-rank test Estimation: Stratified Cox model with Efron's tie handling method	ITT	Censored at the date participant last known to be alive
Key Secondary Analy	ses		
PFS per RECIST 1.1 by BICR	Testing: stratified log-rank test Estimation: Stratified Cox model with Efron's tie handling method	ITT	 CCI censoring rule CCI CCI CCI
Abbreviations: BICR=blind	ed independent central review. ITT=intent	-to-treat: OS=overal	survival: PES=progression-
free survival: RECIST 1.1=	Response Evaluation Criteria in Solid Tun	-10-11-221, 05-07-2121	1 survival, 1 1 S-piogression-

Table 13	Analysis Strategy for Key Efficacy Endpoin	ıts
----------	--	-----

CCI

9.6.2 Statistical Methods for Safety Analyses

Safety and tolerability will be assessed by clinical review of all relevant parameters, including AEs, laboratory tests, vital signs, and ECG measurements.

The analysis of safety results will follow a tiered approach (Table 14). The tiers differ with respect to the analyses that will be performed. Safety parameters or adverse experiences of special interest that are identified a priori constitute "Tier 1" safety endpoints that will be subject to inferential testing for statistical significance with p values and 95% confidence intervals provided for between-group comparisons. Other safety parameters will be considered Tier 2 or Tier 3 based on the observed proportions of participants with an event. Tier 2 parameters will be assessed via point estimates with 95% confidence intervals provided for between-group comparisons; only point estimates by treatment group are provided for Tier 3 safety parameters.

Tier 1 Events

Safety parameters or adverse events of special interest (AEOSI) that are identified a priori constitute "Tier 1" safety endpoints that will be subject to inferential testing for statistical

significance. AEOSI that are immune-mediated or potentially immune-mediated are well documented and will be evaluated separately; however, these events have been characterized consistently throughout the pembrolizumab clinical development program and determination of statistical significance is not expected to add value to the safety evaluation. Finally, the addition of MK-7684A to etoposide/platinum treatments included in the study is not anticipated to be associated with any new safety signals. Therefore, there are no Tier 1 events expected in this study.

Tier 2 Events

Tier 2 parameters will be assessed via point estimates with 95% CIs provided for differences in the proportion of participants with events using the Miettinen and Nurminen (M&N) method [Miettinen, O. and Nurminen, M. 1985], an unconditional, asymptotic method.

Membership in Tier 2 requires that at least 10% of participants in any treatment group show the event; all other AEs and predefined limits of change will belong to Tier 3. The threshold of at least 10% of participants was chosen for Tier 2 events because the population enrolled in this study is in critical condition and usually experiences various AEs of similar types regardless of treatment; events reported less frequently than 10% of participants would obscure the assessment of the overall safety profile and add little to the interpretation of potentially meaningful treatment differences. In addition, Grade 3 to 5 AEs (\geq 5% of participants in 1 of the treatment groups) and SAEs (\geq 1% of participants in 1 of the treatment groups) will be considered Tier 2 endpoints. Because many 95% CIs may be provided without adjustment for multiplicity, the CIs should be regarded as a helpful descriptive measure to be used in safety review, not as a formal method for assessing the statistical significance of the between-group differences.

Tier 3 Events

Safety endpoints that are not Tier 1 or 2 events are considered Tier 3 events. The broad AE categories consisting of the proportion of participants with any AE, a drug-related AE, a serious AE, an AE that is both drug-related and serious, a Grade 3-5 AE, a drug-related Grade 3-5 AE, and discontinuation due to an AE will be considered Tier 3 endpoints. Only point estimates by treatment group are provided for Tier 3 safety parameters.

Safety Tier	Safety Endpoint	95% CI for Treatment Comparison	Descriptive Statistics
Tier 2	Grade 3-5 AE (incidence ≥5% of participants in one of the treatment groups)	Х	Х
	Serious AE (incidence ≥1% of participants in one of the treatment groups)	Х	X
	AEs (incidence $\geq 10\%$ of participants in one of the treatment groups)	X	Х
Tier 3	Any AE		Х
	Any Grade 3-5 AE		Х
	Any Serious AE		Х
	Any Drug-Related AE		X
	Any Serious and Drug-Related AE		X
	Any Grade 3-5 and Drug-Related AE		X
	Discontinuation due to AE		X
	Death		X
	Specific AEs, SOCs (incidence <10% of participants in all of the treatment groups)		Х
	Change from Baseline Results (lab toxicity shift, vital signs)		X
Abbreviati	ons: AE=adverse event; CI=confidence interval; SOC=system or	rgan class.	

Table 14 Analysis Strategy for Safety Parameters

9.6.3 **Statistical Methods for Patient-Reported Outcome Analyses**

This section describes the planned analyses for the PRO endpoints.

Mean Change from Baseline

The time point for the mean change from baseline will be determined based on blinded data review prior to the database lock for any PRO analysis and documented in the sSAP.

To assess the treatment effects on the PRO score change from baseline in the Global Health Status/OoL scale (EORTC OLO-C30 Items 29 and 30), Physical functioning scale (EORTC QLQ-C30 Items 1 through 5), cough (EORTC QLQ-LC13 Item 31), chest pain (EORTC QLQ-LC13 Item 40), dyspnea (EORTC QLQ-C30 Item 8) and EQ-5D-5L visual analog scale, a constrained longitudinal data analysis (cLDA) model proposed by Liang and Zeger [Liang, K-Y. and Zeger, S. L. 2000] will be applied, with the PRO score as the response variable, and treatment, time, treatment by time interaction, and stratification factors used for randomization (See Section 6.3.2) as covariates. The treatment difference in terms of least square (LS) mean change from baseline will be estimated from this model

together with 95% CI. Model-based LS mean with 95% CI will be provided by treatment group for PRO scores at baseline and post-baseline time point.

Time-to-True Deterioration (TTD)

For the TTD endpoint defined in Section 9.4.3, the Kaplan-Meier method will be used to estimate the TTD curve for each treatment group. The estimate of median time to deterioration and its 95% confidence interval will be obtained from the Kaplan-Meier estimates. The treatment difference in TTD will be assessed by the stratified log-rank test. A stratified Cox proportional hazard model with Efron's method of tie handling and with a single treatment covariate will be used to assess the magnitude of the treatment difference (ie, HR). The HR and its 95% CI will be reported. The same stratification factors used for randomization (See Section 6.3.2) will be used as the stratification factors in both the stratified log-rank test and the stratified Cox model.

The approach for the TTD analysis will be based on the assumption of non-informative censoring. The participants who do not have deterioration on the last date of evaluation or do not have a second PRO assessment to confirm deterioration will be censored. Table 15 provides censoring rule for TTD analysis.

Scenario	Outcome
Deterioration documented	Event observed at time of assessment (first deterioration)
Ongoing or discontinued from study without confirmed deterioration	Right censored at time of last assessment
No baseline assessments	Right censored at treatment start date

 Table 15
 Censoring Rules for Time-to-True Deterioration

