1 PROTOCOL SUMMARY

Four Phase 3 studies met prespecified futility criteria for OS or RFS: MK-7684A-003 in metastatic NSCLC with PD-L1 TPS \geq 50% CC MK-7684A-007 in metastatic NSCLC with PD-L1 TPS \geq 1% CC

MK-7684A-008 in ES-SCLC (OS HR, 1.26; 95% CI, 1.00-1.59; presented at Society for Immunotherapy of Cancer 2024), and MK-7684A-010 in adjuvant melanoma (RFS HR, 1.25; 95% CI, 0.87-1.80; presented at Society for Melanoma Research 2024) (data on file). Overall, the lack of efficacy observed with MK-7684A rendered the risk-benefit balance unfavorable, so treatment with this investigational therapy was stopped in all studies.

At implementation of Amendment 05, the below changes apply. The changes listed below supersede any protocol content/instructions from previous amendments.

- Participants with access to approved SOC (eg, immunotherapy, chemotherapy, targeted therapy) should be considered for discontinuation from the study. Those benefiting from atezolizumab, but unable to access it as SOC outside the study, may continue on study and receive treatment with atezolizumab until discontinuation criteria are met. The final required study visit will be the Safety Follow-up Visit.
- Participants who complete study treatment or otherwise meet EOT criteria will be discontinued from the study after the EOT visit and any required safety follow-up visit.
- There will be no follow up for survival status. Participants currently in imaging follow-up or survival follow-up are considered to have completed the study and therefore should obtain imaging and further oncological care as per local SOC. Standard safety reporting should, however, continue, as applicable.
- Participants remaining on study at the time of Amendment 05 should continue to be monitored in the study through the AE reporting period (Section 8.4).

Existing protocol content is retained for historical reference.

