follow-up or in survival follow-up are considered to have completed the study and therefore should obtain imaging and further oncological care as per local standard of care. Participants currently on study treatment will have tumor imaging assessed locally based on the site's standard of care imaging schedule. Scans will not be submitted to the iCRO, and VOP request and central review of imaging will no longer be applicable. PK sampling, anti-drug antibody sampling, and blood for ctDNA analysis will no longer be collected on any participants. PROs will no longer be collected on any participants. Participants on study treatment will need to have safety follow-up after treatment is discontinued (participants will no longer be treated under the study). This safety follow-up will be considered their last visit. Collection of AE and lab parameters for participants remaining in study will continue per SOA. These changes were communicated through the investigator letter dated 08-AUG-2024 and Protocol Clarification Letter dated 13-AUG-2024.

Study Phase	Phase 3
Primary Purpose	Treatment
Indication	Small cell lung cancer
Population	Participants with extensive-stage small cell lung cancer
Study Type	Interventional
Intervention Model	Parallel
	This is a multi site study.
Type of Control	Active Control Without Placebo
Study Blinding	Double-blind with in-house blinding
Blinding Roles	Investigator
	Participants or Subjects
	Sponsor
Estimated Duration of Study	The Sponsor estimates that the study will require approximately 5 years from the time the first participant (or their legally acceptable representative) provides documented informed consent until the last participant's last study-related contact.

Number of Participants:

Approximately 450 participants will be randomized.

Intervention Groups and Duration:

Protocol Amendment 04 implementation: All active participants in the experimental arm (Arm A: MK-7684A) stopped ongoing treatment with MK-7684A and were offered the option to move to the comparator arm (Arm B: atezolizumab monotherapy) for the remainder of the study.

					Regimen/	
					Treatment Period /	
	Intervention	Unit Dose	Dosage	Route of	Vaccination	
Arm Name	Name	Strength(s)	Level(s)	Administration	Regimen	Use
			200 MG/			
			200 MG			
•						
A (Ducto col		MK-7684			02W (D 1 -f	
Amendment		200 mg +			each cycle) until	
04: Arm A		200 mg/20 mL			discontinuation	Test
discontinued)	MK-7684A	vial		IV Infusion	criteria are met	Product
А						

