9 STATISTICAL ANALYSIS PLAN

At implementation of Amendment 05, the below changes apply. The changes listed below supersede any protocol content/instructions from previous amendments.

- Participants with access to approved SOC (eg, immunotherapy, chemotherapy, targeted therapy) should be considered for discontinuation from the study. Those benefiting from atezolizumab, but unable to access it as SOC outside the study, may continue on study and receive treatment with atezolizumab until discontinuation criteria are met. The final required study visit will be the Safety Follow-up Visit.
- Participants who complete study treatment or otherwise meet EOT criteria will be discontinued from the study after the EOT visit and any required safety follow-up visit.
- There will be no follow up for survival status. Participants currently in imaging follow-up or survival follow-up are considered to have completed the study and therefore should obtain imaging and further oncological care as per local SOC. Standard safety reporting should, however, continue, as applicable.
- Participants remaining on study at the time of Amendment 05 should continue to be monitored in the study through the AE reporting period (Section 8.4).

Existing protocol content is retained for historical reference.

Protocol Amendment 04 implementation: based on recommendations of the eDMC following the interim efficacy/safety analysis (data cutoff 04-JUN-2024) which showed that the primary endpoint of overall survival met the pre-specified futility criteria, the study was unblinded, the experimental arm (Arm A: MK-7684A) will be discontinued and all ongoing participants on MK-7684A treatment will be offered the option to move to the comparator arm (Arm B: atezolizumab monotherapy) for the remainder of the study. The prespecified final analysis of the study described in the SAP will not be performed. Safety analysis will be performed at the end of the study. There will be no further analyses for efficacy and ePRO endpoints collected from participants after IA cutoff date.

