9.12 Extent of Exposure

Extent of exposure for a participant is defined as the number of cycles in which the participant receives the study medication infusion (see Section 8.6). Summary statistics will be provided on the extent of exposure for the APaT population.

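### Adverse events are compared between arms only as crude percentages although the AE window follows treatment duration; if time at risk differs by arm the comparison is biased, in a direction the documents do not establish

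*Combined protocol and SAP*

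**What the plan says.** Section 9.6.2 assesses Tier 2 events by "point estimates with 95% CIs provided for differences in the proportion of participants with events", using the Miettinen-Nurminen method. For the broad AE categories, "Only point estimates by treatment group are provided for Tier 3 safety parameters". There are no Tier 1 events. On the intervals, the section says that "the CIs should be regarded as a helpful descriptive measure to be used in safety review, not as a formal method" of testing.

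Treatment in both arms runs until a discontinuation condition is met (Section 4.1). Section 8.4.1 sets AE reporting from randomization to 30 days after study intervention ends. For SAEs the limit is 90 days, or 30 if new anticancer therapy starts.

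Section 9.12 states: "Extent of exposure for a participant is defined as the number of cycles in which the participant receives the study medication infusion". It gives summary statistics for the treated population and is not linked to the AE comparison.

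Under Amendment 04, active Arm A participants "stopped ongoing treatment with MK-7684A and were offered the option to move to the comparator arm" (Section 1.1). The efficacy final analysis was dropped, but "Safety analysis will be performed at the end of the study" (Section 9). Section 9.5.2 keeps participants in their randomized safety group unless they took the wrong intervention for the whole treatment period.

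**The concern.** A difference in crude proportions is a fair comparison of toxicity only if both arms were watched for comparable lengths of time. Here the length of observation is itself an outcome of treatment: progression, toxicity, death or choice ends dosing, and the AE window closes soon after. The arm watched for less time has less opportunity to show an event and looks safer.

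The Amendment 04 action adds an asymmetry. It interrupted or ended assigned treatment in Arm A only, before the end-of-study safety analysis. Nothing in Section 9.6.2, Table 14 or Section 9.12 brings in person-time or time to event. Those parts are readable, so redaction does not explain the gap. The supplemental SAP is not among the documents; it is cited for exploratory analyses, ePROs and pooling of strata, not for this. At stake is whether a reader of the final safety tables can tell a difference in toxicity from a difference in follow-up.

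**Working it through.** **Inputs from the documents.** Crude-proportion comparison (9.6.2, Table 14). AE window to 30 days after last dose (8.4.1), so w = 30/30.4375 = 0.986 months. About 450 participants at 1:1, or 225 per arm (9.9). Chemotherapy for up to 4 three-week cycles, or 12 weeks (4.1, Table 1), so c = 84/30.4375 = 2.76 months. The plan states no exposure or AE-rate figure, so there is none to reproduce. The OS result in the Protocol Summary, "OS HR, 1.26; 95% CI, 1.00-1.59", is internally consistent: √(1.00 × 1.59) = 1.261.

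**Assumptions (not trial data).** Time on treatment T is exponential. The control median is 5.2 months, borrowed from the median PFS that Section 2.2.1.1 cites for the atezolizumab regimen, so μ_B = ln2/5.2 = 0.1333 per month. The stopping-hazard ratio is 1.26, borrowed from the OS hazard ratio, so μ_A = 0.1680. The AE hazard is the same in both arms.

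**1. Mean window.** 5.2/ln2 + 0.986 = 8.5 months in Arm B; 5.2/(1.26 × ln2) + 0.986 = 6.9 months in Arm A.

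**2. Constant AE hazard λ.** Crude proportion = 1 − exp(−λw) × μ/(μ+λ). For 20% in Arm B, λ = 0.0287. Arm A at the same λ gives 1 − 0.9721 × 0.1680/(0.1680 + 0.0287) = 17.0%, a shift of −3.0 points. For 10% and 40% the Arm A values are 8.3% and 35.3%. With a true rate ratio of 1.2 against MK-7684A, Arm A shows 19.8% against 20.0%, or 39.8% against 40.0%: the excess disappears.

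**3. Sensitivity to direction and inputs.** Shift in points, Arm A minus Arm B:

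| Stopping-hazard ratio | Control 10% | 20% | 40% |
|---|---|---|---|
| 0.75 (longer on MK-7684A) | +2.6 | +4.5 | +6.3 |
| 1.00 | 0 | 0 | 0 |
| 1.26 | −1.7 | −3.0 | −4.7 |
| 1.59 | −3.1 | −5.6 | −9.1 |

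At 1.26 with the 90-day SAE window, the shifts are −1.4, −2.5 and −3.9. With a 4.3-month control median and the 30-day window they are −1.6, −3.0 and −4.6.

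**4. Front-loaded hazard.** Let the hazard be λ to week 12 and rλ afterwards: H(t) = λ·min(t,c) + rλ·max(t−c,0). The crude proportion is 1 − E[exp(−H(T+w))]. Mean person-time to first event or window end is ∫exp(−H(t))·P(T+w>t)dt. The overall exposure-adjusted rate is the crude proportion divided by that person-time. At a stopping-hazard ratio of 1.26:

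| Later hazard r | Crude shift at control 10%, 20%, 40% | Overall exposure-adjusted rate ratio (truth: equal hazards) |
|---|---|---|
| 1 | −1.7, −3.0, −4.7 | 1.00 |
| 0.25 | −1.0, −1.8, −2.9 | 1.08 to 1.09 |
| 0.10 | −0.6, −1.1, −1.8 | 1.12 to 1.14 |
| 0 | −0.2, −0.3, −0.6 | 1.18 to 1.20 |

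The crude bias shrinks as events move into the chemotherapy period. A single overall exposure-adjusted rate then errs the other way, because the shorter-exposed arm loses mostly low-hazard person-time.

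**5. Against sampling error.** With equal observed rates and 225 per arm, the Miettinen-Nurminen 95% half-width is 7.4 points at 20% and 9.0 at 40%.

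**The case against.** The strongest reply is that no difference in time at risk has been shown. A reader might infer from the OS hazard ratio and the Arm A stop that exposure was shorter on MK-7684A, so that the crude differences favour it. The documents do not support that. They give no treatment duration, exposure or PFS by arm. OS is not time on treatment, and the lower confidence limit is 1.00. The design hypothesis on PFS pointed the other way. Under Section 9.5.2 switchers appear to stay in Arm A, and Table 4 lists atezolizumab for all participants, so their later time and events may lengthen Arm A's window. Amendment 05 also asks that any participant with access to approved care be considered for leaving the study, in either arm. This part of the objection stands: the direction is unknown.

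It is also true that the plan calls the intervals descriptive, that clinical review carries the safety assessment, that an interim efficacy and safety analysis with a 04-JUN-2024 cutoff preceded the stop, and that the illustrated shifts at a ratio of 1.26 lie inside the half-widths above. These points limit the weight of the concern but do not remove it. The descriptive caveat is given because of multiplicity and does not warn about unequal follow-up. An interim cutoff before the stop does not equalize treatment duration between the arms. A follow-up bias can push many AE terms the same way and does not shrink with sample size.

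**Conclusion.** The concern holds in conditional form. The plan compares AEs only by crude proportions, over windows set by open-ended treatment duration, after an intervention that applied to one arm, and nothing in it shows or adjusts for time at risk. If time at risk differs, the differences and their descriptive intervals are biased: toward fewer events on MK-7684A if its exposure was shorter, and the reverse if it was longer.

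At a stopping-hazard ratio of 1.26 the size runs from about −0.2 to −0.6 points (events confined to the first 12 weeks) to −1.7 to −4.7 points (constant hazard), for control rates of 10% to 40%. This rests on an exponential 5.2-month control median and a stopping-hazard ratio borrowed from OS, neither of which is an exposure result from this trial. Chemotherapy-period toxicity is affected least and later events most. This is a worthwhile, inexpensive improvement, not evidence that the safety comparison is wrong in a known direction.

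**What to change.** In Section 9.6.2 and Table 14, keep the crude percentages. For each Tier 2 term and each broad AE category, add one of the following:

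- cumulative incidence of the first event by arm, with death as a competing event, and the between-arm difference with 95% CI at stated times; or
- exposure-adjusted incidence rates given separately for the chemotherapy period (Cycles 1-4) and the later period.

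Do not use a single overall exposure-adjusted rate. With front-loaded chemotherapy events it would show a false excess of roughly 10% to 20% on the shorter-exposed arm.

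For the between-arm comparison, apply one calendar cutoff to both arms, at or before the Arm A stop. The documents give no unblinding date, but the 04-JUN-2024 data cutoff or the 08-AUG-2024 investigator letter would serve. Report later AEs separately. In Section 9.12, add duration of exposure and AE observation time in months by arm.

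The cost is SAP wording and one extra set of tables from data already collected. Late time points will be less precise, and events after the cutoff leave the comparison.
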